12.6 Quality assurance

The IBCSG conducts trials according to the ICH Good Clinical Practice (GCP) guidelines. The Study Data Manager reviews each Case Report Form as they are received. In addition, the Study Chair and/or IBCSG Medical Reviewer reviews each case at specific timepoints. The IBCSG conducts periodic audit visits to ensure proper trial conduct, verify compliance with GCP, and perform source data verification.

Data Management manuals are available from the IBCSG website (www.ibcsg.org).

13 Administrative considerations

## 1. Introduction

### 1.1 Background

In 2003 IBCSG initiated a suite of three complementary tailored treatment investigations, the SOFT, TEXT and PERCHE trials, designed to answer questions concerning adjuvant treatment for premenopausal women with endocrine-responsive early breast cancer: 1) What is the role of ovarian function suppression (OFS) for women who remain premenopausal and are treated with tamoxifen? 2) What is the role of aromatase inhibitors for women treated with OFS? 3) What is the role of chemotherapy for women treated with OFS plus oral endocrine therapy?

The conduct of these randomized phase III trials required world-wide participation through collaboration of the Breast International Group (BIG) network and the North American Breast Cancer Groups. Pfizer is the primary pharmaceutical industry partner and Ipsen provides triptorelin outside of North America.

Over a 7.5-year period from 2003 to 2011, 5742 premenopausal women were enrolled at over 500 centers in 27 countries on 6 continents in:

TEXT (Tamoxifen and Exemestane Trial): designed to determine the role of AIs for women who receive OFS from the start of adjuvant therapy;

SOFT (Suppression of Ovarian Function Trial): designed to determine the role of OFS and the role of AIs for women who remain premenopausal after completion of (neo)adjuvant chemotherapy, or who are premenopausal following surgery and tamoxifen alone is a reasonable treatment option;

PERCHE (Premenopausal Endocrine-Responsive Chemotherapy): designed to determine the value of adding chemotherapy to combined endocrine therapy with OFS plus oral endocrine therapy.

TEXT and SOFT successfully enrolled the targeted number of patients. PERCHE closed prematurely in 2006 with only 29 patients enrolled (25 of 29 were co-enrolled in TEXT; (Regan et al., Ann Onc 2008).

Completion of TEXT and SOFT enrollment was anticipated within 5 years and first reporting about 7 years after the trials' initiation. However the characteristics of the enrolled patients differ from those anticipated in the protocols, and patients' outcomes are better than expected, necessitating an adaptation of the trials' analysis plans, in protocol amendments released in 2011. The original designs of TEXT and SOFT and the adaptations to overcome these challenges and ensure timely answers to questions concerning adjuvant treatment for premenopausal women with endocrine-responsive early breast cancer were described recently (Regan et al., Breast 2013).

[figure not shown]
### 1.2 Trial Designs

The designs of TEXT and SOFT are summarized below.

## TEXT (IBCSG 25-02 / BIG 3-02)

Title:	Tamoxifen and Exemestane Trial (TEXT): A phase III trial evaluating the role of exemestane plus GnRH analogue as adjuvant therapy for premenopausal women with endocrine responsive breast cancer.
Patient Population:	Premenopausal women (estradiol (E2) levels in the premenopausal range) with histologically proven, resected breast cancer with ER and/or PgR positive tumors (ER and/or PgR ≥ 10%).
Entry:	Patients should be randomized within 12 weeks after surgery prior to commencing any adjuvant systemic therapy.
Activation Date:	04Aug03 (First patient randomized 7Nov03)
Target Accrual:	2639 patients
Closure Date:	11Mar11 (Last patient randomized 7Apr13)
Final Accrual:	2672 patients

### TEXT Schema:

\* Randomization prior to receiving any adjuvant systemic therapy

\*\*CT (chemotherapy) is determined by investigator/patient choice and if used, should begin at the same time as triptorelin.

[figure not shown]
\*\*\*Tamoxifen or exemestane should start after adjuvant chemotherapy has been completed or approximately six to eight weeks after the initiation of triptorelin, whichever is later.

IBCSG 25-02 (TEXT) is an international, non-blinded, randomized phase III trial designed to investigate the efficacy the aromatase inhibitor (AI) exemestane with OFS, achieved by long-term use of GnRH analogue, compared with tamoxifen+OFS. TEXT focuses the AI question on premenopausal patients whom the physician feels OFS is most appropriate from the start of adjuvant therapy. Eligibility required enrollment within 12 weeks of definitive surgery and excluded patients who had already received any (neo)adjuvant chemotherapy or endocrine therapy. Randomization used 1:1 allocation and stratified by whether adjuvant chemotherapy was planned (no; yes), and number of positive nodes (0; 1 or more). Patients would either receive no chemotherapy or commence chemotherapy at the same time as GnRH analogue is initiated. Patients had to use GnRH analogue for at least 6 months and then could change to permanent OFS with surgery or radiation at any time thereafter.

## SOFT (IBCSG 24-02 / BIG 2-02)

Title:	Suppression of Ovarian Function Trial (SOFT): A phase III trial evaluating the role of OFS and the role of exemestane as adjuvant therapies for premenopausal women with endocrine-responsive breast cancer.
Patient Population:	Premenopausal women (estradiol (E2) levels in the premenopausal range†) with histologically proven, resected breast cancer with ER and/or PgR positive tumors (ER and/or PgR ≥ 10%) who have received either no chemotherapy or remain premenopausal following completion of adjuvant and/or neoadjuvant chemotherapy.
Entry:	Patients who do not receive chemotherapy should be randomized within 12 weeks after surgery; such patients must have E2 levels in the premenopausal range following surgery. Patients who have received adjuvant and/or neoadjuvant chemotherapy should be randomized within 8 months of the final dose of chemotherapy as soon as premenopausal status is confirmed; such patients must have E2 levels in the premenopausal range between 2 weeks and 8 months after the final dose of chemotherapy.
Activation Date:	04Aug03 (First patient randomized 17Dec03)
Target Accrual:	3000 patients
Closure Date:	31Jan11 (Last patient randomized 27Jan11)
Final Accrual:	3066 patients

### SOFT Schema:

\* Patients may have received tamoxifen or an anti-aromatase agent prior to randomization

\*\* OFS = ovarian function suppression (triptorelin for 5 years OR surgical oophorectomy OR ovarian irradiation)

IBCSG 24-02 (SOFT) is an international, three-arm, non-blinded, randomized phase III trial designed to investigate the role of OFS and the role of the AI exemestane, originally planned with three primary comparisons: tamoxifen+OFS versus tamoxifen alone; exemestane+OFS versus tamoxifen alone; and exemestane+OFS versus tamoxifen+OFS. SOFT focuses the OFS question on those who biologically would be most likely to benefit, i.e., women with endocrine-responsive breast cancer with premenopausal status either after completion of (neo)adjuvant chemotherapy or following surgery alone.

Eligibility required enrollment either: (a) within 8 months of the final dose of chemotherapy once premenopausal status was confirmed by estradiol levels (e.g., patients with temporary chemotherapy-induced amenorrhea who regained premenopausal status within 8 months were eligible); or (b) within 12 weeks of definitive surgery if no adjuvant chemotherapy was to be given. Patients could have received adjuvant oral endocrine therapy (but not GnRH analogues) for up to 8 months prior to randomization. The 8-month criterion was an early protocol amendment (from 6 months) to overcome logistical challenges of enrolling a patient who presented after regaining premenopausal status at a 6-months post-chemotherapy standard-of-care visit.

Randomization used 1:1:1 allocation, and was stratified according to prior (neo)adjuvant chemotherapy (yes;no), lymph node status (0; 1+) and intended method of OFS (GnRH analogue, oophorectomy; ovarian irradiation). For patients randomized to receive OFS, the use of GnRH analogue, bilateral oophorectomy or bilateral ovarian irradiation was by patient preference and patients who began with GnRH analogue could opt to undergo surgery or irradiation at any time.

### **1.2.1 Design Commonalities**

As a planned suite of trials, a majority of trial design features were common to both trials. Briefly, the trials enrolled premenopausal women with histologically-proven, resected, hormone receptor-positive (defined as ER $\geq$ 10% and/or PgR $\geq$ 10%) early invasive breast cancer. Premenopausal status was defined by estradiol levels in the premenopausal range according to institutional parameters. The tumor was to be confined to the breast and axillary lymph nodes without detected metastases elsewhere. Patients must have had proper local-regional treatment for primary breast cancer with no known residual loco-regional disease. Study visits were every 3 months during year one, every 6 months during the next 5 years, and yearly follow-up thereafter.

The oral endocrine therapy was either tamoxifen or the steroidal AI exemestane. OFS was by GnRH analogue triptorelin administered 4-weekly for 5 years, bilateral surgical oophorectomy, or bilateral ovarian irradiation (with biochemical confirmation of cessation of ovarian function after 2 months).

### **1.2.2 Original statistical design assumptions and sample size considerations**

TEXT planned enrollment was 1845 patients. The design projected that 4.5 years of uniform accrual, plus 2.4 years of additional follow-up, would be sufficient to observe the target of 396 DFS events, which would provide 80% power to detect 25% reduction in hazard with exemestane+OFS versus tamoxifen+OFS (HR=0.75; 79.8% versus 74.1% 5-year DFS, respectively) using a 2-sided 0.05  $\alpha$ -level logrank test and assuming exponential distribution of DFS. Four interim analyses prior to the final analysis were planned. By November 2007, 2039 of the planned 1845 patients had enrolled, and enrollment was suspended. Because of the faster-than-expected enrollment rate and lower-risk characteristics of enrolled patients than anticipated, Amendment 2 (Jul08) re-opened enrollment with an increased target sample size of 2639 patients. A revised estimate of 80% 5-year DFS in the tamoxifen+OFS control group (with corresponding 25% reduction in hazard to 84.6% 5-year DFS for exemestane+OFS) was hypothesized based on the 2007 overview analysis of GnRH analogues in which the 5-year breast cancer recurrence was around 18% among patients treated with GnRH analogue plus tamoxifen. With the observed enrollment pattern and revised hazard rates, the increased sample size was projected to reach the target of 396 DFS events within 0.5 years of the original design, or 7.4 years since first enrollment.

SOFT planned enrollment was 3000 patients for the 3 arms. The design projected that 5 years of uniform accrual, plus 1.9 years of additional follow-up would be sufficient to observe the target of 783 DFS events (522 per pairwise comparison) to have 80% power to detect a 25% reduction in hazard relative to control 5-year DFS of 67% (HR=0.75; 74.1% versus 67.0% 5-year DFS; 2-sided  $\alpha=0.0167$ ). If tamoxifen+OFS would result in a 25% reduction in hazard to 74.1% 5-year DFS, then power was 68% to detect a further 25% reduction with exemestane+OFS to 79.8% 5-year DFS. Four interim analyses prior to the final analysis were planned.

From the outset, the protocols planned to combine the data of TEXT with the two arms of SOFT comparing exemestane+OFS versus tamoxifen+OFS. Differences in the two trials with respect to selection and treatment for women who received chemotherapy (i.e., TEXT enrolled patients following surgery and used concurrent GnRH analogue and chemotherapy, while SOFT enrolled patients who remained premenopausal following chemotherapy and initiated OFS after completion of chemotherapy) were taken into account in the combined analysis plan. The statistical power of such a combined comparison (at the two-sided  $\alpha=0.05$  level) would be at least 88%, 98% and 99% to detect a 20%, 25%, and 30% reduction in hazard, respectively, with exemestane+OFS versus tamoxifen+OFS under the protocol assumptions about accrual duration and additional follow-up.

### 1.2.3 Adaptations in the statistical design and analysis plans

As of October 2010, the overall DFS event rates—blinded to treatment assignment—were substantially lower than originally anticipated: approximately 1.7% and 2% per year versus the protocol-specified 6% and 8% per year in TEXT and SOFT, respectively. IBCSG projected an additional 7 and 13 years of follow-up to observe the targeted 396 and 783 DFS events in TEXT and SOFT, respectively (at median follow-up of 10.5 and 15 years). Increasing the sample size could hasten reaching the required events, but finances constrained this possibility.

The Steering Committee considered this delay to be unacceptably long (reporting 14 and 20 years after first enrollment versus 6.9 years originally-anticipated). The Committee decided to change the timing of analysis from “event-driven” to “time-driven” with a planned data cut-off during the third quarter of 2013, when the median follow-up should be at least 6 and 5 years in TEXT and SOFT, respectively. It was recognized that an analysis with fewer events than targeted would substantially reduce statistical power for the original protocol-planned primary objectives (approximately 60% in TEXT and 35% in SOFT to detect 25% reductions in hazards, assuming the October 2010 event rates continued). Therefore amendments of the TEXT and SOFT protocols (July 2011) revised the analysis plans for the first reporting of the trial objectives:

1. **AI Question:** the primary analysis comparing exemestane+OFS versus tamoxifen+OFS would implement the originally-planned combined analysis of TEXT and SOFT. The power of such a combined comparison (two-sided  $\alpha=0.05$  level) would be at least 95%, 84% and 63% to detect a 30%, 25% and 20% reduction in hazard, respectively, with exemestane+OFS.
2. **OFS Question:** the primary analysis from SOFT would focus on the unique comparison of tamoxifen+OFS versus tamoxifen alone, tested at the two-sided  $\alpha=0.05$  level. IBCSG estimated power to be at least 80%, 69%, 52% and 34% to detect 33.5%, 30%, 25% and 20% reductions in hazard, respectively, with tamoxifen+OFS.

These power calculations assumed a data cut-off in the third quarter of 2013 and persistence of the October 2010 DFS event rates, which project 250 DFS events in TEXT and 280 DFS events in SOFT (about 93 per group under the null hypothesis) at the time of data cut-off. The revised analysis plans removed planned interim efficacy analyses. The revised analysis plans removed planned interim efficacy analyses.

The Steering Committee's decision was endorsed by the IBCSG DSMC. These committees did not receive, nor did the IBCSG Statistical Center have knowledge of, outcome data according to treatment group prior to this decision. The first report of the combined analysis of the **AI Question** is anticipated in mid-2014. The report of the **OFS Question** from SOFT is anticipated in late 2014 after about 6 additional months of follow-up and a median follow-up of at least 5 years is reached.

Patient follow-up will continue and updates of efficacy results are planned approximately every two years after the first reports.

### **1.3 First Results**

#### **1.3.1 AI Question**

After a median follow-up of 68 months (5.7 years), DFS events were reported for 514 (11%) of 4690 patients in the ITT population. Patients assigned E+OFS had statistically significantly reduced hazard of a DFS event vs. patients assigned T+OFS (HR=0.717; 95% CI, 0.602 to 0.855; P=0.0002). The estimated 5-year DFS was improved at 91.1% vs. 87.3% among patients assigned E+OFS vs. T+OFS. The reduction in hazard with E+OFS vs. T+OFS was consistently observed for secondary endpoints of breast cancer-free interval and distant recurrence-free intervals, although at this point in follow-up a reduction in hazard of death was not observed.

In this analysis, 30.2% of patients continue on protocol-assigned treatment. 30.6% and 29.4% of patients assigned to E+OFS and T+OFS have had grade 3-4 targeted AEs reported, of which hot flashes/flushes, musculoskeletal symptoms and hypertension were the most frequently reported

#### **1.3.2 OFS Question**

After a median follow-up of 67 months (5.6 years), DFS events were reported for 299 (14.7%) of 2033 patients in the ITT population. T+OFS non-significantly reduced hazard of a DFS event vs. T (HR=0.83; 95% CI, 0.66 to 1.04; P=0.10). The estimated 5-year DFS among patients assigned T+OFS was 86.6% (95% CI, 84.2% to 88.7%) versus 84.7% (95% CI, 82.2% to 86.9%) among patients assigned T. The relative effects of T+OFS vs. T were consistent between the two chemotherapy strata; as expected, the absolute difference at 5 years was more notable among patients who received prior chemotherapy. The reduction in hazard with T+OFS vs. T was consistently observed for the secondary endpoints of breast-cancer-free interval and distant recurrence-free interval. 106 (5.2%) deaths were reported, and on average there was a non-significantly reduced hazard of death; with all except 10 deaths among patients who received prior chemotherapy, the reduction in hazard was more apparent among this cohort of patients

At the time of the analysis, 26% of patients continued on protocol-assigned treatment. 31% and 24% of patients assigned to T+OFS and T have had grade 3-5 targeted AEs reported, of which hot flashes/flushes, musculoskeletal symptoms and hypertension were the most frequently reported.

#### **1.3.3 Numbers of DFS events, deaths and median follow-up by trial**

For the AI Question analysis, the TEXT ITT population had 285 DFS events and 101 deaths reported, after median follow-up of 6 years (data cut-off, 31Aug13).

At the time of the OFS Question analysis, the 3 arms of the SOFT ITT populations had 412 DFS events and 164 deaths reported, after median follow-up of 5.6 years (data cut-off, 31Mar14).

## 2. Efficacy Analysis Plans

### 2.1 Protocol Objectives

Based on revised statistical analysis plans in the 2011 amendments (i.e., SOFT Amendment 2 (24Aug11); and TEXT Amendment 3 (24Aug11)):

#### 2.1.1 Primary Objective

AI Question: To evaluate the efficacy of exemestane+OFS compared with tamoxifen+OFS, across both trials combined, as adjuvant endocrine therapy for premenopausal women with endocrine-responsive early invasive breast cancer.

OFS Question: To evaluate the role of OFS+tamoxifen compared with tamoxifen alone, as adjuvant endocrine therapy for premenopausal women with endocrine-responsive early invasive breast cancer.

#### 2.1.2 Secondary Objectives

- Assess overall survival, breast cancer-free interval, and distant recurrence-free interval
- Assess quality of life (see separate analysis plan)
- Investigate sites of first treatment failure
- Assess late side effects of early menopause
- Assess the incidence of second (non-breast) malignancies and causes of death without cancer event
- TEXT: Investigate patient and tumor features that may contribute to inter-individual variability of responsiveness to GnRH analogue plus exemestane and GnRH analogue plus tamoxifen (see separate analysis plan)

## 2.2 Updated Analyses

Rather than presenting results by trial, the analyses will continue to be organized as:

- AI Question (E+OFS vs T+OFS), jointly for the two trials;
  - Summarize by 4 cohorts
  - Summarize by trial also
- OFS Question (T+OFS vs T), reporting all three arms

The analysis will secondarily focus on the subgroup of HER2-negative disease. The main reason is the clinical relevance of separating the subgroups of HER2-negative and positive disease in current practice and trial design. We also previously observed heterogeneity of treatment effects according to HER2 status, and the HER2-positive subgroup presents challenges because HER2-directed therapy changed during the conduct of the trials and HER2-directed therapy had different timing in TEXT and

SOFT chemotherapy cohorts (starting after randomization in TEXT, starting and mostly completing prior to randomization in SOFT).

## 2.2 Analysis Populations

The updated analysis will continue to use an intention-to-treat (ITT) approach. During the first analyses, there was one SOFT T+OFS patient who was included in the AI Question ITT population, but then excluded from the OFS Question ITT population (243007). **In updated analyses, this patient will remain in the ITT populations as previously analyzed.**

AI Question: The AI Question ITT population will include

- All patients randomized in TEXT (exemestane+OFS and tamoxifen+OFS);
- SOFT patients randomized to the two OFS-containing arms (exemestane+OFS and tamoxifen+OFS).

OFS Question: The OFS Question ITT population will include

- SOFT patients randomized to the two tamoxifen-containing arms (tamoxifen+OFS and tamoxifen alone).
- SOFT patients randomized to exemestane+OFS.

## 2.3 Endpoint Definitions

Endpoint definitions remain the same as in the first report.

Per IBCSG standard, the date of DFS event is the date a proven recurrence was first suspected. **Since the first trial report**, the 2425-RC Form SOP was clarified that in cases with multiple proven sites of first recurrence (within 2 months of each other), that the date first suspected should be the earliest of suspected dates from among those proven sites (which may not necessarily correspond to the site with the earliest proven date).

## 2.4 Follow-up

As in the first analysis, median follow-up is calculated from the Kaplan-Meier estimate of overall survival, with the event/censoring indicator inverted (i.e. alive as event and dead as censored).

In the first analysis, the visit cut-offs were 31Aug13 and 31Mar14. Updated results were anticipated to be presented every two years thereafter until the last patient enrolled has been followed for at least 10 years.

For the first update, concurrent visit cut-offs (of 31Dec16) and database locks (**04May17**) are planned. The visit cut-off is selected because almost all patients will have at least 6 years follow-up (except those final patients randomized during Q1 2011).

## 2.5 Tests and Estimates

As in the first analysis, the primary objectives will be investigated by comparing DFS between two treatment groups using two-sided stratified logrank test ( $H_0: DFS_1=DFS_2$ ;  $H_a: DFS_1 \neq DFS_2$ ), with an overall experiment-wise  $\alpha=0.05$  (i.e.,  $\alpha=0.05$  for AI Question analysis; and  $\alpha=0.05$  for OFS Question analysis). The test statistic and p-value will be taken from the stratified Cox PH model score test. Hazard ratios (AI Question: E+OFS / T+OFS; OFS Question: OFS+T / T) will be estimated from a stratified Cox PH model, with two-sided Wald 95% CIs. Kaplan-Meier estimates of the DFS distributions will be calculated for each of the treatment arms, with reporting of the **8yr DFS (MFU is 7.9y in SOFT and 9.1y in TEXT so 8yr estimates appropriate for both trials)**; the SEs will use Greenwood's formula and the pointwise 95% CIs will be obtained using complementary log-log transformation of the SDF.

The E+OFS vs T comparison will be included with estimation of HR (95% CI) for E+OFS / T, but no hypothesis testing is planned. The 8yr DFS would also be summarized.

In the first OFS Question analysis, the primary analysis model included only the 2 treatment groups; it is **now planned that the model for HR estimates will include all 3 treatment groups**, using contrasts to obtain the pairwise score tests.

We will check the proportional hazards assumption by visually assessing the plot of  $\log(-\log(\text{survival}))$  versus log of survival time for parallelism. This will be done overall, and according to strata.

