Two-sided alpha level	.0167	.0167	.0167
Power	.80	.80	.80
Required number of events for two arms*	861	522	343
Accrual rate for two arms (pts/year)	400	400	400
Total accrual time (yrs)	5.5	5	4 .5
Sample size (two arms)	2200	2000	1800
Total study duration with 4 interim + 1 final analyses (yrs)*	9.8	6.9	5.4
Total sample size (all 3 arms)	3300	3000	2700

* Under the alternative hypothesis with 4 interim analyses and 1 final analysis [41].

For planning purposes, we will target a 25% reduction in hazard for each of the three comparisons. This will require recruitment for the three arms of **3000 patients** (600 patients per year for 5 years with 1.9 years of additional follow up). Accrual of premenopausal patients with ER-positive tumors to IBCSG Trials VI (N+) and VIII (N-) averaged 222 per year. Applying the 15.6% rate of maintaining menses following chemotherapy to this cohort, we anticipate approximately 35 patients per year from IBCSG institutions. Global participation including the Breast International Group (BIG) and the US Intergroup is required to successfully complete this trial.

The same operating characteristics apply to the second comparison (OFS plus exemestane versus tamoxifen alone) and to the third comparison (OFS + exemestane versus OFS + tamoxifen), when testing for an improvement in 5-year DFS from the baseline value of 67%. If one assumes a 25% reduction in hazard due to the addition of OFS to tamoxifen (and thus an estimated 74.1% 5-year DFS for the OFS + tamoxifen arm), then a further 25% reduction in the hazard for OFS + exemestane compared with OFS + tamoxifen (to 79.8% 5-year DFS) would be detected with 68% power, if the final analysis is performed at 6.9 years from the activation of the study.

The originally planned sample size was 3000. It was projected that 5 years of accrual, plus 1.9 years of additional follow up would be sufficient to observe the 783 target number of DFS events (522 needed for each pairwise comparison). This number of events would provide 80% power to detect a hazard ratio of 0.75 for GnRH + tamoxifen versus tamoxifen alone (74.1% versus 67.0%)

5-yr DFS, respectively) using a 2-sided, 0.0167 level test (adjusting for multiple tests). The study opened to enrollment in August 2003. In January 2011, enrollment was closed with 3066 patients randomized. Due to agreements with pharmaceutical partners and financial constraints, it is not possible to increase patient enrollment.

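### SAP 2.5 labels alpha as overall experiment-wise 0.05, but each of two primary questions is tested at a full two-sided 0.05, so control is per question only (about 0.095 jointly at a single look)

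*SAP*

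**What the plan says.** SAP 2.5 compares DFS by two-sided stratified logrank test "with an overall experiment-wise" alpha of 0.05. The bracket that follows gives 0.05 "for AI Question analysis; and" again 0.05 "for OFS Question analysis). The test statistic and p-value will be taken from the stratified Cox PH model score test".

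SAP 2.1.1 lists both questions as primary:
- "AI Question: To evaluate the efficacy of exemestane+OFS compared with tamoxifen+OFS, across both trials combined"
- "OFS Question: To evaluate the role of OFS+tamoxifen compared with tamoxifen alone"

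Protocol 9.2 caps the experiment-wise alpha for the primary objectives at 0.05. Protocol 9.3 describes how the original SOFT design met that cap for three pairwise comparisons, "using a 2-sided, 0.0167 level test (adjusting for multiple tests"). The 2011 revision (protocol 9.3, SAP 1.2.3) tests the OFS comparison at two-sided 0.05 and powers the combined SOFT and TEXT comparison at two-sided 0.05. In protocol 2.1, only the exemestane+OFS versus tamoxifen comparison is marked as having become secondary. The OFS and AI comparisons both remain under SOFT's primary objectives.

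**The concern.** An experiment-wise level is a bound on the chance of any false positive across the family of primary tests. Two tests at a full 0.05 each, with no split, hierarchy or gatekeeping, do not meet a bound of 0.05. The wording appears to be left over from the original design, where a split (0.0167 for each of three tests) did support it.

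What is at stake is the claim made to readers, not a result. Someone who relies on the label would credit the two primary tests with joint error control that they do not have.

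There is a related, secondary gap. SAP 2.5 applies the same tests at the update as in the first analysis, and SAP 2.6.3.2 tabulates p-values again. The OFS test has already been done once, with P=0.10 (SAP 1.3.2). The documents supplied do not say whether a p-value below 0.05 at the update would be confirmatory or nominal.

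**Working it through.** **1. Is 0.05 per question really the level used?** The documents state it, and the power figures confirm that it is not a slip for 0.025. SAP 1.2.3 projects "250 DFS events in TEXT and 280 DFS events in SOFT (about 93 per group under the null hypothesis"). Two SOFT arms therefore give D = 280 × 2/3 = 186.7 events, and the AI Question gives D = 250 + 186.7 = 436.7. Power = Φ(√D/2 × |ln HR| − z), with z = 1.960 for alpha 0.05 and 2.241 for alpha 0.025. For example, the OFS Question at HR 0.75 and alpha 0.05 gives 6.832 × 0.2877 − 1.960 = 0.005, so power is 0.502.

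| Question | HR | Stated | At 0.05 | At 0.025 |
|---|---|---|---|---|
| OFS | 0.665 | 80% | 79.6% | 70.7% |
| OFS | 0.70 | 69% | 68.3% | 57.7% |
| OFS | 0.75 | 52% | 50.2% | 39.1% |
| OFS | 0.80 | 34% | 33.2% | 23.7% |
| AI | 0.70 | 95% | 96.1% | 93.1% |
| AI | 0.75 | 84% | 85.2% | 77.8% |
| AI | 0.80 | 63% | 64.5% | 53.6% |

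The OFS row of stated powers is from SAP 1.2.3: "IBCSG estimated power to be at least 80%, 69%, 52% and 34"%. All seven stated values are within 2 points of the calculation at 0.05. At 0.025 the OFS values are about 9 to 13 points too low.

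**2. Did the original split support the label?** Yes: 3 × 0.0167 = 0.0501, which is 0.05 up to rounding.

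**3. Joint type I error now, single look, both nulls true.**
- Upper bound: 0.05 + 0.05 = 0.10.
- Independent tests: 1 − 0.95² = 0.0975.
- Allowing for the shared arm: SOFT tamoxifen+OFS is the comparator for the AI Question and the experimental arm for the OFS Question, so the two statistics are negatively correlated. The AI analysis had 514 events, 285 of them in TEXT (SAP 1.3.1 and 1.3.3), which leaves 514 − 285 = 229 from SOFT.
  - Same cut-off for both: with 1:1:1 allocation the correlation is −0.5 × √(229/514) = −0.334. The bivariate normal probability that either |Z| exceeds 1.96 is 0.0945.
  - Actual cut-offs (AI 31Aug13; OFS 31Mar14 with 299 events, SAP 1.3.2): the correlation is −(229/8)/√((514/4) × (299/4)) = −0.292, and the probability is 0.0952.

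**4. What the label would require.** A split of 0.025 per question gives 0.0482 with the correlation of −0.334 and 0.0494 if independent. The last column of the table shows what that would cost in power.

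**5. Repeat testing (illustration only).** The documents give no event counts for the update. Assume that events grow in proportion to SOFT median follow-up, from 5.6 years (SAP 1.3.3) to 7.9 years (SAP 2.5). The first look then held 5.6/7.9 = 0.71 of the update's events. Two looks, each at 0.05, with correlation √0.71 = 0.84 give about 0.075 for the OFS Question. Assumed fractions of 0.8 and 0.6 give 0.071 and 0.080.

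**The case against.** The strongest reply is that nothing is hidden and the levels are reasonable. The same sentence that uses the label gives 0.05 for each question. Protocol 2.1.3 makes the AI comparison the primary analysis for TEXT, while protocol 9.3 and SAP 1.2.3 make the OFS comparison the primary analysis from SOFT. On that view each trial has one primary test at 0.05, and experiment-wise means per trial.

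This stands as a defence of the levels. It does not rescue the label. Protocol 2.1 keeps both comparisons among SOFT's own primary objectives, SAP 2.1.1 lists both as primary, and the original plan treated experiment-wise as spanning several tests. A reader might infer that the 0.05s are errors for 0.025, or that the SAP miscalculates alpha. The documents support neither: the stated powers match 0.05, and no stated number is wrong.

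A second reply is that protocol 9.2 sits in an amended text where old and new wording are merged, so its current status is not certain. That is fair, and it is why the two documents should be reconciled together. Changing SAP 2.5 alone would leave it contradicting protocol 9.2 as it reads.

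A third reply concerns repeat testing. The original SAP was not supplied and may define the status of updates. The documents also separate the first report from later updates (protocol 9.3, SAP 1.2.3), although they stop short of calling the later p-values nominal. The two-look figure rests on an assumed event count. A reader might infer that the programme has a known overall error rate across all its looks. It does not: the update counts are not given, and further updates are planned about every two years. For the AI Question, which gave P=0.0002 at the first report, the matter has little practical bearing.

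**Conclusion.** The label in SAP 2.5, and the matching cap in protocol 9.2, describe a property that the amended design does not have. Type I error is controlled at 0.05 per question. Taken as one family at a single look, with both nulls true, it is about 0.095 (0.0945 to 0.0952 with the shared arm, 0.0975 if independent). These figures rest on the first-report event counts, 1:1:1 allocation and the usual large-sample normal approximation.

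This is a minor correction of a stated property, not an arithmetic error or a fault in the tests. A reader might infer that the first results are in doubt. They are not: AI P=0.0002 passes and OFS P=0.10 fails at either 0.05 or 0.025.

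The missing status of the update p-values is a secondary point. It is conditional on what the original SAP says, and the 0.075 for OFS is an illustration under an assumed information fraction.

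**What to change.** In SAP 2.5, replace the label and its bracket with: *two-sided alpha=0.05 for each question (AI as the TEXT primary analysis, OFS as the SOFT primary analysis), with no experiment-wise control across the two questions*. Reconcile protocol 9.2 with the same wording so that the two documents agree.

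Add to SAP 2.5, unless the original SAP already assigns their status: *p-values at this and later updates are nominal, because the tests repeat those of the first report*.

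No joint-error figure is needed in the SAP. If the 0.095 is quoted, mark it as applying to a single look. If a two-look figure is quoted, state the assumed information fraction beside it.

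The cost is two sentences in the SAP and a matching edit to protocol 9.2. The downside is that the stated error control becomes less favourable and the update p-values carry less weight.
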